1 BACKGROUND AND PROJECT RATIONALE

A low body mass index (BMI) has been described as an independent risk factor for mortality in subjects with chronic obstructive pulmonary disease (COPD), while the association was strongest in patients with severe COPD ¹. Additionally, weight loss in the course of the disease was associated with increased mortality ².

A low fat free mass index (FFMI) was also associated with increased overall and COPD-related mortality, even in subjects with normal BMI ³. FFMI seems to be a better predictor of disease severity regarding the degree of chronic dyspnea, forced expiratory volume in 1 second (FEV1), FEV1/forced vital capacity (FVC) ratio and stage of disease than BMI ⁴. Patients with the constellation of abdominal obesity, normal weight and low muscle mass have an increased cardiometabolic risk ⁵. FFMI also correlates with quality of life ⁶. Sarcopenic obesity (SO) is associated with worse physical performance and higher systemic inflammatory burden compared with other body composition phenotypes in COPD ⁷. Sarcopenia affects 15% of patients with stable COPD and impairs function and health status. Sarcopenia does not impact on response to pulmonary rehabilitation (PR), which can lead to a reversal of the syndrome in select patients ⁸. Body composition evaluation is useful for the assessment of COPD patients referred to pulmonary rehabilitation and should be routinely performed ⁹. A well-balanced diet is beneficial to all COPD patients, not only for its potential pulmonary benefits, but also for its proven benefits in metabolic and cardiovascular risk ¹⁰.

If our hypothesis proves to be true, the clinical consequence would be the need to systematically include nutritional assessment / therapy and other measures to reduce malnutrition and sarcopenia in the clinical routine of treating COPD patients to reduce overall risk of acute exacerbation of COPD (AECOPD) and improve quality of life.

The study is of risk category A since there are no relevant risks for participating patients (the study poses no additional risks to the patients compared to routine care).

2 PROJECT OBJECTIVES AND DESIGN

2.1 Hypothesis and primary objective

The primary objective is to investigate the association between physical activity, malnutrition and sarcopenia and the occurrence of AECOPD / the evolution of the COPD assessment test (CAT) over 1 year in a cohort of COPD patients. We hypothesize that being malnourished and/or sarcopenic at baseline and a decline of FFMI over time is associated with an increased rate of AECOPD and an increased (or increasing) CAT score.

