2.2 Primary and secondary endpoints

The primary endpoint is the rate of exacerbation depending on the explanatory variables FFMI, hand grip strength (HGS) and C-reactive protein (CRP), measured at baseline, after 6 and after 12 months. We will examine the correlation between the evolution of FFMI/HGS/CRP and the occurrence of AECOPD / the evolution of the CAT.

Secondary endpoints include further parameters from our COPD cohort, such as physical activity and further biochemical markers (e.g., protein, albumin, 25-OH vitamin D3), which will be analyzed by descriptive statistics (including cross-sectional and longitudinal analyses).

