3.3 Study procedures

All patients will be followed using the THC procedure as previously described ^{11,12}. Specifically, the CAT score is measured once per week and patients answer questions on a daily basis that aim at the early detection of AECOPD. The study duration is one year per patient.

In addition, we will measure body composition (e.g., FFMI and fat share) by direct segmental multi-frequency bioelectrical impedance analysis (BIA) and/or dual-energy X-ray absorptiometry (DXA), HGS (with a dynamometer) and biochemical parameters (e.g., CRP, protein, albumin, 25-OH vitamin D3). These measurements will take place at baseline and after 6 and 12 months. Furthermore, patients are provided with a pedometer to record step count and/or an accelerometer to record overall movement/distance traveled. This might be complemented by a standardized sit-to-stand physical test at each visit (baseline, 6 and 12 months). We will assess the nutritional status by standardized questionnaires (Nutritional Risk Screening [NRS] 2002; in case of malnutrition, "Nutritional Assessment" according to local guidelines) and provide nutritional support/therapy by professional personnel. In the final analysis, receipt of nutritional support/therapy will be one parameter stratified for. Nutritional parameters will be assessed at baseline and after 6 and 12 months. Schedule of assessment in appendix 1.

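### Physical activity is part of the primary objective (2.1), but 2.2 makes it a descriptive secondary endpoint and 4.1 names no model for it

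*Combined protocol and SAP*

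**What the plan says.** Section 2.1 sets the aim: "The primary objective is to investigate the association between physical activity, malnutrition and sarcopenia and the occurrence of AECOPD". The evolution of the CAT over one year is named alongside AECOPD as outcome. The hypothesis that follows is narrower and leaves activity out: "We hypothesize that being malnourished and/or sarcopenic at baseline and a decline of FFMI over time is associated with an increased rate of AECOPD", together with a higher or rising CAT score.

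Section 2.2 defines the primary endpoint without activity: "The primary endpoint is the rate of exacerbation depending on the explanatory variables FFMI, hand grip strength (HGS) and C-reactive protein (CRP", each measured at baseline, 6 and 12 months. It adds that the correlation of the course of these three variables with AECOPD and CAT will be examined. Activity comes in the next paragraph: "Secondary endpoints include further parameters from our COPD cohort, such as physical activity and further biochemical markers", and the method for that group is given as "which will be analyzed by descriptive statistics (including cross-sectional and longitudinal analyses".

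Section 3.3 says how activity is captured: "patients are provided with a pedometer to record step count and/or an accelerometer to record overall movement/distance traveled". It gives no recording period and no summary measure.

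Section 4.1 bases the sample size on the change in FFMI against the exacerbation rate. It then names linear regression for FFMI over time, Andersen-Gill and joint models for FFMI and AECOPD, and mixed models or GEE for FFMI and CAT. Activity does not appear in 4.1.

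**The concern.** The sections give an analyst different instructions. Section 2.1 asks for an association between activity and two outcomes. Section 2.2 places activity in a lower tier with a descriptive method, and 4.1 supplies no model. An analyst who follows 2.2 and 4.1 can summarise activity by visit and finish with no regression estimate or confidence interval for the first exposure named in the primary objective.

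The alternative is to choose the metric, time window, outcome and model after the data are in. An activity result obtained that way would carry little weight, even in an exploratory study. Activity data are already to be collected, and suitable model types are already named for FFMI, so both outcomes can be avoided at low cost.

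**Working it through.** **1. The plan's own figure.** Inputs from section 4.1: r = 0.30, 80% power, two-sided 5%. By Fisher's z for one correlation:

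n = ((z₀.₉₇₅ + z₀.₈₀) / atanh(r))² + 3 = ((1.960 + 0.842) / 0.3095)² + 3 = 84.93, rounded up to 85.

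Power at n = 85 is Φ(0.3095 × √82 − 1.960) = Φ(0.843) = 80.0%. The 85 reproduces. It belongs to the change in FFMI against the exacerbation rate and to nothing else.

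**2. Tracing each variable through the plan.**

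| Variable | 2.1 objective | 2.1 hypothesis | 2.2 | 4.1 |
|---|---|---|---|---|
| Physical activity | yes | no | secondary, descriptive | no model |
| Malnutrition status | yes | yes | not named | no model |
| Sarcopenia status | yes | yes | not named as such | not named as such |
| FFMI and its change | not named | yes (decline) | primary explanatory variable | sample size and all models |
| HGS, CRP | not named | not named | primary explanatory variables, correlation stated | no model |

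Activity is the only variable that is in the primary objective and is also expressly given a descriptive method. For malnutrition status, HGS and CRP, 4.1 is silent. For activity, 2.1 and 2.2 conflict.

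**3. Does anything else reconcile them?** Section 3.3 covers measurement only. The schedule in Appendix 1 has no row that names activity. Section 4.2 deals with enrolment and dropout. None of them supplies an outcome, model or summary measure for activity.

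**4. Which tier suits an activity analysis?** This step assumes r = 0.30 for activity as well, which the documents do not state.

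- Two primary associations with alpha split equally (0.025 each, two-sided): n = ((2.241 + 0.842) / 0.3095)² + 3 ≈ 102.2, so 103 patients. Power at 85 is Φ(0.3095 × √82 − 2.241) = 71%.
- Two associations each at 5% with no split: the family-wise error is 1 − 0.95² = 9.75% if the tests are independent.

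Keeping activity in the primary tier would therefore cost either power or error control. A secondary tier, reported by estimate and interval, leaves the 85 untouched.

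**The case against.** The strongest reply is that activity is a stray term in one sentence. The hypothesis, the primary endpoint, the sample size and the clinical consequence described in section 1 all leave it out, and section 2.3 calls the study exploratory. This stands in part. What lacks an analysis is a stated part of the objective, not a stated hypothesis, and that lowers the weight of the point. It does not remove the conflict, because 2.1 still promises the association.

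A second reply is that the parenthesis in 2.2 on cross-sectional and longitudinal analyses leaves room for, say, a correlation of activity with AECOPD or CAT. That is possible, so it would be wrong to say that no estimate of any kind could be produced. But the parenthesis qualifies descriptive statistics and names no outcome, model or activity measure.

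A reader might also infer stronger things that the documents do not support:

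- *Activity values cannot be pooled.* The and/or wording in 3.3 permits different devices in different patients. It equally permits the same device, or both, for everyone.
- *Only one of three exposures lacks an estimate.* Malnutrition status has no named model either, nor do HGS and CRP, so a count of one in three misleads.
- *The 85 patients give 80% power for activity.* That figure is for one unadjusted correlation with an assumed r. It does not carry over to a coefficient in an Andersen-Gill or mixed model. Section 4.2 also counts refusals and later dropouts together in its 15%, so 85 complete activity records are not assured.
- *Leaving activity out confounds the FFMI result.* The documents give no basis for this. Activity may be a mediator, and adjusting for it would then change the quantity being estimated.

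**Conclusion.** The point holds as an inconsistency between 2.1 on one side and 2.2 and 4.1 on the other. One exposure named in the primary objective has no planned model-based estimate of its association with AECOPD or CAT. Nothing else in the documents resolves this.

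The size is modest. No stated hypothesis goes untested for this reason, the sample size calculation is correct, and the planned FFMI analyses are not called into question. The conclusion rests on reading the sections as written, with descriptive statistics in 2.2 taken in its usual sense. If the sponsor meant the longitudinal analyses in 2.2 to include a regression of outcome on activity, the remaining fault is that this regression is not specified and that the tiers in 2.1 and 2.2 still disagree.

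**What to change.** Reconcile the three sections together:

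- **2.1:** move physical activity from the primary to a secondary objective. Calling the analysis secondary without this change would leave 2.1 and 2.2 in disagreement.
- **2.2:** except activity from the sentence that assigns descriptive statistics.
- **4.1:** add separate secondary models with baseline activity as predictor, Andersen-Gill for AECOPD and a mixed model for CAT. Report estimates with 95% confidence intervals, labelled exploratory.
- **Metric:** fix in advance one activity measure that is available for all patients, for example mean daily step count over a fixed period, and state that period in 3.3.
- **Main FFMI model:** keep activity out of it, or show the model with and without activity, because activity may be a mediator.

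If the sponsor does not want the analysis, delete activity from the primary objective in 2.1 and leave 2.2 as it stands.

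The cost is a few sentences across these sections, one metric to be fixed in advance, and one further exploratory association to report. No extra patients are needed, because the analysis makes no power claim. If fixing the metric means changing which device patients receive, that is a change of procedure, and the sponsor should check whether section 5.5 requires it to be submitted as an amendment. The missing models for malnutrition status, HGS and CRP could be supplied in the same revision, since this fix alone does not cover them.

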2.2 Primary and secondary endpoints

The primary endpoint is the rate of exacerbation depending on the explanatory variables FFMI, hand grip strength (HGS) and C-reactive protein (CRP), measured at baseline, after 6 and after 12 months. We will examine the correlation between the evolution of FFMI/HGS/CRP and the occurrence of AECOPD / the evolution of the CAT.

Secondary endpoints include further parameters from our COPD cohort, such as physical activity and further biochemical markers (e.g., protein, albumin, 25-OH vitamin D3), which will be analyzed by descriptive statistics (including cross-sectional and longitudinal analyses).

2.3 Project design

A national, monocentric, prospective, observational, exploratory cohort study.

3 PROJECT POPULATION AND STUDY PROCEDURES

3.1 Project population, inclusion and exclusion criteria

Inclusion: any patient with COPD GOLD stage B or higher giving written informed consent to participate. The study population will consist of our current telehealth care (THC) cohort of COPD patients as well as newly recruited COPD patients.

Exclusion: any patient who is unable to provide informed consent or to follow the trial procedures. Insufficient knowledge of the trial language is therefore a reason of exclusion.

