4 STATISTICS AND METHODOLOGY

4.1. Statistical analysis plan

A sample size of 85 patients is envisaged to be able to detect a significant association (expected correlation coefficient $r=0.30$) between Δ FFMI (1 year vs. baseline) and the patients' exacerbation rate with 80% power at a 5% significance level (two-sided).

The evolution of the FFMI will be analyzed using linear regression. The association between the FFMI and the occurrence of AECOPD will be evaluated using the Andersen-Gill formulation of the Cox proportional hazard model as well as joint modeling useful for the analysis of recurrent time-to-event data (exacerbation) with time-varying predictors (FFMI). The association between

FFMI and CAT will be estimated using linear mixed models or alternately generalized estimating equations.

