4.2. Handling of missing data

The patients expected to be enrolled in the current study consist of patients from our previous THC cohort willing to participate in this extension study (approx. 100 patients). Assuming a dropout rate of 15% (including patients not willing to participate to the extension study as well as patients dropping out in the course of the study), we are expecting to enroll 85 patients in the study. Potential dropouts beyond 15% will not be replaced. If a patient withdraws her/his consent during the course of the study, no further data will be collected. However, data that have been collected before withdrawal will be used for the final analysis.

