6 FURTHER ASPECTS

6.1 Overall ethical considerations

Refined prediction of AECOPD leading to timely intervention will positively influence the QoL of the individual study participant. Results from the study are thought to be generalizable among COPD patients. No incidental findings with immediate relevance to the study participant are expected to be made, and genetic findings are anyway precluded in this observational cohort study. The study design is perfectly suited to longitudinally track different clinical parameters and to assess the evolution of the CAT. The time effort that the participants have to take is absolutely reasonable.

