6.2 Risk-Benefit Assessment

The study poses no additional risks to the patients compared to routine care. The patients can benefit from the study through earlier recognition of clinical deterioration, thus allowing for earlier therapeutic intervention and attenuation (or even prevention) of disease exacerbation.

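### Existing telehealth patients and new referrals are analysed together with no term for cohort source, a possible confounder, and sections 3.1/3.2 and 4.2 disagree on who is enrolled (minor)

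*Combined protocol and SAP*

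**What the plan says.** - **Who is enrolled.** Section 3.1: "The study population will consist of our current telehealth care (THC) cohort of COPD patients as well as newly recruited COPD patients". Section 3.2 makes the established cohort the main source and adds patients referred from daily practice, without numbers. Section 4.2 describes one source only: "The patients expected to be enrolled in the current study consist of patients from our previous THC cohort willing to participate". It starts from about 100 cohort patients and, after a 15% loss, arrives at 85.
- **What they receive.** Section 3.3: "All patients will be followed using the THC procedure as previously described". This means a weekly CAT and daily questions meant to detect exacerbations early.
- **What monitoring is expected to do.** Section 6.2 says participants may benefit from earlier recognition of deterioration, "thus allowing for earlier therapeutic intervention and attenuation (or even prevention) of disease exacerbation".
- **How the data are analysed.** Section 4.1: "A sample size of 85 patients is envisaged", based on a correlation of 0.30 between one-year FFMI change and exacerbation rate, 80% power and a two-sided 5% level. The models are Andersen-Gill and joint models for exacerbations, and mixed models or GEE for CAT. No covariate for cohort source or prior THC is named. The only stratification factor named anywhere is nutritional support (section 3.3).
- **Scope.** Section 6.1: "Results from the study are thought to be generalizable among COPD patients".

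**The concern.** New and existing patients share one time zero but probably not one monitoring history. Read together, sections 3.1 to 3.3 imply that a newly referred patient begins THC at study entry, whereas a cohort patient has already been in it. If monitoring changes exacerbations, as section 6.2 expects, source is related to the outcome. If new referrals also differ from cohort patients in FFMI, HGS or CRP, or in how these change, source is related to the predictor too. It is then a confounder, and part of the difference between the groups would be reported as an effect of body composition or inflammation.

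Two further points follow. A reader of section 4.2 would not know that a second group is in the analysis set. And every participant is telemonitored, so the observed exacerbation rate is a rate under telemonitoring.

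**Working it through.** **1. The plan's own figure.** Inputs from section 4.1: r = 0.30, 80% power, two-sided 5%. By Fisher's z,

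N = ((1.960 + 0.842) / atanh(0.30))² + 3 = (2.8016 / 0.30952)² + 3 = 84.93, rounded up to 85.

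Power at 85 is 80.0%. The figure of 85 is correct and not in dispute. Section 4.2 agrees: 100 × 0.85 = 85, all from the cohort.

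**2. Inputs the documents do not give.** The share of new patients, the size of any THC start effect, and any difference in predictors between sources. Everything in steps 3 and 4 rests on assumed ranges.

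**3. FFMI change and exacerbation rate (the powered association).** Let w be the share of new patients, q = w(1 − w), and dX and dY the differences between sources in FFMI change and in outcome, in within-source SD. With within-source correlation r,

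r_pooled = (r ± q·dX·dY) / √((1 + q·dX²)(1 + q·dY²)).

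| Assumption | Pooled r | Power at N = 85 |
|---|---|---|
| True r = 0.30, w = 0.3, dX = 0, dY = 0.5 | 0.30 / √1.0525 = 0.292 | 77.9% |
| True r = 0, w = 0.1, dX = dY = 0.5 | 0.0225 / 1.0225 = 0.022 | – |
| True r = 0, w = 0.3, dX = dY = 0.5 | 0.0525 / 1.0525 = 0.050 | – |
| True r = 0, w = 0.3, dX = dY = 0.8 | 0.1344 / 1.1344 = 0.118 | – |
| True r = 0.30, w = 0.3, dX = dY = 0.5, same direction | 0.3525 / 1.0525 = 0.335 | 88.4% |
| As above, opposite direction | 0.2475 / 1.0525 = 0.235 | 58.3% |

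The first row matters most for interpretation: when source is unrelated to FFMI change, pooling creates no false correlation and only dilutes a true one.

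**4. FFMI and CAT change.** Assume p = 15% to 50% new patients, a THC start effect e of −1 to −3 CAT points, an FFMI difference d of 0.25 to 0.5 SD between sources, and an SD of CAT change of 5 points. With q = p(1 − p),

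- slope bias = q·d·e / (1 + q·d²)
- false r = q·d·e / √((1 + q·d²)(25 + q·e²))

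Smallest case (p = 0.15, d = 0.25, e = −1): slope bias −0.0319 / 1.008 = −0.03 points per SD of FFMI. Largest case (p = 0.50, d = 0.5, e = −3): slope bias −0.375 / 1.0625 = −0.35, and |r| = 0.375 / √(1.0625 × 27.25) = 0.07. With d = 0.5 and e = −3, |r| is about 0.04 at p = 0.15 and 0.06 at p = 0.30.

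For scale, the standard error of r at N = 85 is about 1/√82 = 0.11, so 0.07 is about 0.6 standard errors.

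**5. Cost of adjusting.** With one covariate, N − 3 becomes N − 4: the required N is 81.93 + 4 = 85.93, that is 86. Power at 85 is Φ(√81 × 0.30952 − 1.960) = Φ(0.826) = 79.6%. With two covariates it is 79.1%.

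**The case against.** The strongest case against runs as follows. The objective, endpoint and models (sections 2.1, 2.2, 4.1) concern associations, and the distortion of those is small. The largest CAT figure, 0.07, needs half the sample to be new, although section 3.2 makes the existing cohort the main source and section 4.2 expects it to supply all 85. If 4.2 governs, the mixing disappears. The larger shifts for exacerbations need source to differ in both FFMI change and outcome, and no such difference is reported. The THC start effect is assumed: section 6.2 is risk-benefit wording about all participants and gives no size. The study is declared exploratory, and section 3.3 calls nutritional support one stratification parameter, which leaves room for others.

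Most of this stands and sets the priority. It does not remove the point, because the protocol itself expects monitoring to act on its primary outcome, source is not named as a factor, and the sections on enrolment contradict each other.

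A reader might infer four stronger things that the documents do not support:

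- *That the mean one-year CAT change is spoiled.* Under the assumptions in step 4 it would shift by p × e, from −0.15 (0.15 × −1) to −1.5 (0.50 × −3) points, but section 4.1 plans no analysis that reports mean CAT change as a result.
- *That cohort patients have long been monitored without interruption.* Sections 3.1, 3.2 and 4.2 call the cohort current, established and previous, and give no individual THC duration. Nor do they say that start dates are on file.
- *That the whole plan ignores new patients.* Sections 3.1 and 3.2 describe them; only 4.2 leaves them out.
- *That telemonitoring invalidates wider use of the association.* It limits transfer of the absolute event rate. It limits the association only if THC modifies it, which nothing in the documents shows.

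**Conclusion.** The point holds as a minor one. Sections 3.1 and 3.2 enrol two kinds of patient, section 4.2 plans for one, and these must be reconciled. If new patients are enrolled, cohort source is a possible confounder of the FFMI, HGS and CRP associations with exacerbations and CAT, and section 4.1 leaves it unadjusted.

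The size cannot be determined from the documents. For CAT change, the assumed ranges give a false |r| of at most about 0.07. For exacerbations, 10% to 30% new patients and differences of 0.5 SD in both variables give 0.02 to 0.05; only large differences of 0.8 SD in both, at 30% new patients, bring it to about 0.12. A true r of 0.30 could be moved to 0.235 or 0.335 in the 0.5 SD case at 30% new patients, and power moves visibly because the design has no reserve above 80%. All of this requires source to be linked to the predictor as well as to the outcome; otherwise there is only slight dilution. That new patients start THC at entry is an inference from sections 3.1 to 3.3, though a firm one.

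**What to change.** 1. Record cohort source (established or new) and THC start date for every patient.
2. In section 4.1, add source as a covariate in the Andersen-Gill and joint models, and source with source-by-time in the CAT model.
3. Add a sensitivity analysis restricted to established THC patients.
4. Correct section 4.2 so that it names both sources, in line with 3.1 and 3.2. If the intention is cohort patients only, correct 3.1 and 3.2 instead; items 2 and 3 then fall away.
5. In section 6.1, state that the results, in particular event rates, apply to telemonitored COPD patients of GOLD stage B or higher.

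Cost: one or two degrees of freedom, which at N = 85 means power of about 79.6% or 79.1% instead of 80.0% on the plan's correlation approximation; one or two extra data items; and a narrower stated scope. The restricted analysis will be smaller (at an assumed 30% new patients, 85 × 0.7, or about 60), so it should be read for consistency of the estimate and not for significance.
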